5.2 Procedures for Handling Incorrectly Randomized Subjects

Subjects who fail to meet the inclusion/exclusion criteria should not, under any circumstances, be randomized into the study. There can be no exceptions to this rule.

A subject who does not meet the eligibility criteria but who is randomized in error, and is identified before dosing, should be withdrawn from the study and another subject should be enrolled and receive the same treatment.

Sponsor's Medical Monitor should be notified if an ineligible subject is dosed.

5.3 Treatments

It is the Investigator's responsibility to establish a system for handling the IMP, to ensure that:

- Deliveries of such products are correctly received by a responsible person.
- Deliveries are recorded and IMP is handled and stored safely and properly.
- IMP provided for this study will be used only as directed in the study protocol.

The study personnel will account for all IMP received at the site, dispensed to the subject, and returned to the pharmacy/site. Any discrepancies should be documented, investigated, and appropriately resolved.

Any unused IMP are accounted for and returned to the IMP manufacturer (Basel), or destroyed by the hospital pharmacy of the research site. Receipt of the IMP and confirmation of destruction in writing will be obtained by each study site after study termination.

5.4 Identity of Investigational Medicinal Product

The drug substance is d-lysergic acid diethylamide (LSD). The identity of the IMP is presented below:

Table 1: Identity of Investigational Product

IMP	Dose
MM-120	LSD-tartrate 0.029mg (corresp. 0.020 mg LSD), ethanol 0.16 g, aqua pur ad 1 mL
Placebo	Ethanol 0.16 g aqua pur ad 1 mL

Substance preparation and quality control: Analytically LSD d-tartrate salt will be obtained from [REDACTED]. LSD will be formulated as an oral drinking solution in dark vials. A Swissmedic approved Good Manufacturing Practice (GMP) facility ([REDACTED]) will prepare the IMP and the placebo (solution without MM-120 in identical vials), as well as perform the individualized packaging based on the randomization list, labeling and quality control (QC).

5.4.1. Packaging and labelling

The IMP will be packaged and labelled in accordance with current Good Manufacturing Practices (cGMPs) and provided to the sites. The shipping of the IMP to the sites will be in accordance with Good Distribution Practice (GDP). Re-supply will be executed as needed by the same manufacturer.

Labelling of the IMP will be performed in accordance with cGMPs and will comply with the applicable laws and regulations of the countries in which the study sites are located.

It is the responsibility of the Investigator to ensure that accurate accountability records are maintained throughout the study.

5.5 IMP, Concomitant, and Post-Study Treatment(s)

IMP will be administered twice a week, every 3 to 4 days. The IMP can be administered at the clinic on Day 1 or at home after Day 1 per PI decision under supervision of study personnel (i.e., the Investigator or delegate). Dosing/dispensing is based on the delegation log by authorized study personnel. The IMP cannot be provided to the subjects to take home. However, instead of administering the IMP at the clinic, IMP may also be brought to the subject's home by one of the study investigators or delegates on the delegation log and administered at home. A supportive person of the subject's choosing may be present with the subject in the home. Dosing at home is not allowed on Day 1 or if protocol procedures cannot be completed at the home visit or under urgent safety measures per Section 7.11. Furthermore, adverse effects and the use of concomitant medication are recorded based on the delegation log by authorized study personnel and the diary is checked; all safety assessments will be obtained and AEs recorded per Schedule of Events. Administration at home is mainly intended to facilitate trial conduct. If a remote visit is conducted due to any reason related to the COVID-19 pandemic, notification must be sent to the Medical Monitor's dedicated email address and Urgent Safety Measures as outlined in this protocol must be followed.

Apart from paracetamol/acetaminophen (not more than 3 g per day) if needed, no concomitant medication or therapy will be allowed that may interfere with the IMP (see Section 5.5.1). The subject should be instructed that no other medication is allowed, including herbal remedies, vitamins, mineral supplements, and over the counter products, without the consent of the Investigator.

The administration of all medication, (including the IMP), should be recorded in the appropriate sections of the eCRF. Treatment adherence will be assured by supervised administration of the IMP by the Investigator or delegate. The dose, time, and date of administration of the IMP will be recorded on the IMP accountability log and checked by the monitor at monitoring visits. Unused IMP should be destroyed at the site or returned to the manufacturer.

5.6 Withdrawal from Study

Subjects may be withdrawn at any time. Once dosing has occurred, every attempt should be made to continue assessments to ensure the safety of the subject. Specific reasons for withdrawing a subject should be documented in the eCRF, and include, but are not limited to:

- Subject's decision
- The Investigator or Sponsor judges that it is in the best interest of the subject to stop study treatment due to any abnormality compromising subject safety
- Pregnancy
- Severe noncompliance to the study protocol as judged by the Investigator and/or the Sponsor.

Subjects who prematurely discontinue may be replaced, per Sponsor decision. Subjects will not be allowed to re-enter the study.

5.6.1. Procedures for withdrawal of a subject from the study

Subjects are free to withdraw their consent to participate in the study at any time, without prejudice. Such subjects will always be asked about the reason(s), and the presence of any adverse events. If possible, subjects who withdraw from the study after dosing and before completion should be seen by an Investigator, and undergo the assessments and procedures scheduled for the follow-up visit/end of study visit. Adverse events should be followed up.

5.7 Audits and Inspections

Authorized representatives of the Sponsor, Health Authority, or an Ethics Committee may perform audits or inspections at the site, including source data verification. The purpose of an audit or inspection is to examine all study-related activities and systematically and independently document, to determine whether these activities were conducted, and data were recorded, analyzed, and accurately reported according to the protocol, GCP, guidelines of the ICH, and any applicable regulatory requirements. The Investigator will contact the Sponsor immediately if contacted by a regulatory agency about an inspection at the center.

6. COLLECTION OF STUDY VARIABLES

6.1 Schedule of Events

The study assessments are described in the sections below and the timing of these assessments are detailed in the study plan.

Table 3: Schedule for study specific assessments

Time in Weeks	Screening	Baseline ^g	Dosing begins	Dosing Period (20 µg MM-120) ^h 6-week Blinded Treatment				End of Study/ Early Termination ^h
Arm 1 - placebo Arm 2 – MM-120	Up to 4 weeks prior to Day -1	Day -1	Day 1	Week 2 (Pre-dose on 3rd dosing visit) Day 8 (+/- 1 day)	Twice weekly* Dosing (+/- 1 day) (Starts Day 1)	Every 2 weeks (first dose of the week) (Starts Day 15)	Week 6 (before final dose unless otherwise noted)	Week 10 follow-up or final visit if withdrawing from study
Informed consent	X							
Demography	X							
Medical/surgical history	X							
Inclusion/exclusion criteria	X	X						
Pregnancy test (for women without documentation of sterilization)	X		X		X ⁸			X
Physical examination	X						X	X
Weight and BMI ^a	X						X	X
Height	X						X	X
Vital signs ^b	X	X	X		X		X	X
Clinical Laboratory Tests ^c	X					X	X	X
Pharmacokinetics			X ⁷					

Pharmacodynamics (5D-ASC, & MEQ30) ^d			X				X ^{1,5}	
12-lead ECG ^e	X			X ⁴			X ⁴	
Cognitive Performance Test		X					X	
CAARS ^f	X	X				X	X	X
ASRS (done prior to dosing)		X				X	X	X
AISRS, CGI-S	X	X			X		X	X
MINI	X							
C-SSRS screening/baseline	X							
C-SSRS since last visit (SLV)		X	X			X	X	X
VAS				X ⁶				
Check daily diary	X	X	X			X	X	X
Randomization				X				
MM-120 or placebo administration				X		X ³		
Adverse events	X	X	X			X	X	X
Concomitant medication	X	X	X			X	X	X

Abbreviations: 5D-ASC = 5 dimensions of altered states of consciousness scale; AISRS = Adult ADHD Investigator Symptom Rating Scale; ASRS = Adult ADHD Self-Report Scale; BMI = body mass index; BP = blood pressure; CAARS = Conners' Adult ADHD Rating Scale; CGI-S = Clinical Global Impression Scale; C-SSRS = Columbia-Suicide Severity Rating Scale; ECG = electrocardiogram; MEQ30 = Mystical Experience Questionnaire (30-item); VAS = Visual Analog Scale.

* Twice weekly dosing will occur every 3 to 4 days (e.g., every Monday and Wednesday) with a \pm 1 day window and will be coordinated to occur at the same time as the Week 2 visit and the every 2 weeks visits when possible.

- a Body mass index will be calculated using body height at screening.
- b Vital signs (pulse, BP, HR, RR, and body temperature) will be performed at every visit.
- c Clinical laboratory samples for chemistry and hematology and urine samples for drug screen and pregnancy testing will be collected pre-dose.
- d Pharmacodynamic scales are completed at home up to 6 hours after dosing.
- e Subject should be supine for 5 minutes prior to ECG collection.
- f CAARS-O-RS conducted at screening. All other assessments will be with the CAARS-L-SR.
- g Baseline visit is within 3 days of Day 1 (\pm 1 day).
- h Following day 1 dosing, all visits may be conducted remotely per Investigator decision as long as all activities can be conducted per protocol, e.g., calibrated blood pressure cuff, calibrated weight scale, ECG, computer cognitive scale. Any visit conducted remotely due to COVID-19 requires Sponsor Medical Monitor and operations team notification and conduct under urgent safety measures and all protocol deviations captured in EDC designated COVID-19 deviation.

X¹ subject fills out forms at home.

X² [REDACTED] 6 weeks of blinded treatment on MM-120 / placebo; may be dosed at home per Investigator decision.

X³ 2 hours after dosing.

X⁴ 6 hours after dosing.

X⁵ Collected repeatedly 0-6 hours after dosing.

X⁶ PK samples will be collected at pre-dose, 0.5, 1, 2, 3, 4, and 6 hours post-dose.

X⁷ During treatment period, pregnancy testing will occur predose at each dosing visit or a minimum of once weekly.

Subjects excluded during screening may be rescreened once in consultation with the Sponsor's Medical Monitor, when the reason for meeting an exclusion is likely to resolve (e.g., the subject had an exclusionary acute infection that is resolving, or a medication taper is taking longer than 28 days). If a subject is rescreened, the subject must be reconsented to participate in the study.

D-LYSERGIC ACID DIETHYLAMIDE (LSD) D-TARTRATE (MM-120)
Protocol MMED007

Mind Medicine, Inc.

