Study Design	
This study is a multi-center, randomized, double-blind, placebo-controlled Phase 2a study of low dose MM-120 (20 μg) compared with a placebo administered for 6 weeks (twice a week on a 3/4-day schedule [\pm 1 day]).
 
Low dose MM-120 (20 μg) is about 20% of the dose typically consumed for recreational psychedelic purposes.
 
There will be a 1:1 randomization, double-blind, to MM-120 or placebo with the aim to reach 26 evaluable subjects in each of the 2 arms at Week 6.
 
There will be 2 arms:
 
 • Arm 1-Placebo: a total of 26 subjects will receive a placebo identical in appearance to the investigational medicinal product (IMP) administered orally twice weekly (e.g., Tuesday/Friday) for 6 weeks. • Arm 2-MM-120: a total of 26 subjects will receive 20 μg of MM-120 administered orally twice weekly for 6 weeks. 
Subjects will be evaluated at Baseline, Week 1, Week 6 and at Week 10, for AISRS and CGI-S by trained study personnel; the primary endpoint will be based on evaluation of AISRS at Baseline and at Week 6.
 
Screening and Baseline visits:
 
 • Potential study subjects who provide informed consent will have eligibility

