### **2.1.3 Visit windows**

As subjects do not always adhere to the protocol visit schedule, the following rules will be applied to assign actual visits to analysis visits for all parameters.

The visit windows and the target days for each visit (including unscheduled ones) are listed below in Table 2. The reference day is Day 1, the first day of dosing, as defined in Section 11.1.1. If a subject has two or more actual visits in the same visit window, the visit closest to the target day will be used for recording data from that visit in the EDC. The data collected scheduled and unscheduled visit(s) will be mapped to visits as follows: If two actual visits are equidistant from the target day within a visit window, the later visit will be used; if more than one value falls on the same day then the last sequential number in sdtm will be used.

All assessments corresponding to both scheduled and unscheduled visits will be included in subject listings.

Table 2 contains analysis visit windows and the target study days for the following selected visits: Baseline, Week 2, Week 4, Week 6 and Week 10; lower and upper limits associated with each visit will cover all possible days from randomization to end of study allowing mapping all the applicable assessments to the visits.

As vital signs and Columbia-Suicide Severity Rating Scale (C-SSRS) will be evaluated at each visit (twice weekly), a different time windowing will be applied to those variables only (see Table 3). Daily diary contains daily sleep quality/ duration rating assessments that will be computed at each week by the mean of values recorded between lower and upper limits (days) specified in Table 4, no target study day will be considered.

For parameters, where Time Interval Upper Limit for Baseline is equal to 1, please apply a rule of time defined in section 11.1.1.8 for Baseline.

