**Table 3: Scheduled Visit Window and Mapping of Assessments for Vital Sign, C-SSRS**

Scheduled Visit Number	Scheduled Time point	Label on output	Target Study Day*	Time Interval Lower Limit (Day*)	Time Interval Upper Limit (Day*)
Baseline	Baseline	Baseline - Week 1 D1	1	No Lower limit	1
Week 1 D5	Week 1 D5	Week 1 D5	5	2	6
Week 2 D8	Week 2 D8	Week 2 D8	8	7	10
Week 2 D12	Week 2 D12	Week 2 D12	12	11	13
Week 3 D15	Week 3 D15	Week 3 D15	15	14	17

Scheduled Visit Number	Scheduled Time point	Label on output	Target Study Day*	Time Interval Lower Limit (Day*)	Time Interval Upper Limit (Day*)
Week 3 D19	Week 3 D19	Week 3 D19	19	18	20
Week 4 D22	Week 4 D22	Week 4 D22	22	21	24
Week 4 D26	Week 4 D26	Week 4 D26	26	25	27
Week 5 D29	Week 5 D29	Week 5 D29	29	28	31
Week 5 D33	Week 5 D33	Week 5 D33	33	32	34
Week 6 D36	Week 6 D36	Week 6 D36	36	35	38
Week 6 D40	Week 6 D40	Week 6 D40	40	39	EOT
Week 10 Follow-up/Final visit for withdrawals	Week 10 Follow-up/Final visit for withdrawals	Week 10 Follow-up/ Final visit for withdrawals	70	EOT+1	No upper limit

\*Relative to Study Day 1

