#### **10.12.1.1 Subgroup analysis**

TEAEs, SAEs, AEs related to the study drug and AEs leading to premature treatment discontinuation will be tabulated on SAF by preferred term (PT) by treatment phase as follows:

- **Days of dosing:** all AEs occurred on same date/visit of treatment but only during or after administration of study drug (with time on or after treatment administration). Week 1 D1 (Dose 1), Week 1 D5 (Dose 2), Week 2 D8 (Dose 3), Week 2 D12 (Dose 4), Week 3 D15 (Dose 5), Week 3 D19 (Dose 6), Week 4 D22 (Dose 7), Week 4 D26 (Dose 8), Week 5 D29 (Dose 9), Week 5 D33 (Dose 10), Week 6 D36 (Dose 11), Week 6 D40 (Last dose 12);

This information will be pooled in summary table, i.e. all AEs occurred on/after all doses: first, second etc. until last dose; as well as will be summarized separately, i.e. AEs occurred on/after each dose: on/after first dose, on/after second dose etc. and until on/after last dose.

- **Non-dosing days:** (a) all AEs with the date different from treatment administration date/visit defined above and until Week 10 Follow-up visit. (b) all AEs which occurred prior to study drug administration (with time before administered dose) on dosing days.

This information will be pooled in summary table, i.e. all AEs occurred between doses: first and second, second and third etc. until Week 10 Follow-up visit (EOS) or until Early Termination (ET) whatever comes earlier, as well as will be summarized separately, i.e. split by periods between doses: Dose 1 - Dose 2, Dose 2 - Dose 3, Dose 3 - Dose 4, Dose 4 - Dose 5, Dose 5 - Dose 6, Dose 6 - Dose 7, Dose 7 - Dose 8, Dose 8 - Dose 9, Dose 9 - Dose 10, Dose 10 - Dose 11, Dose 11 - Dose 12, Dose 12 | last administered Dose - EOS | ET.

In case of missing dates, the rules defined in Section 11.3.3 will be applied. In case of missing time of the AE or the treatment administration on the same day, the AE will be considered as occurred after the treatment administration, meaning will be summarized in 'Days of dosing' category.

Frequency statistics will be presented by treatment group. The summary tables will be presented in descending order according to their incidence in the active treatment group of 'Days of dosing' treatment phase (e.g., individual preferred term with the highest number of occurrences appear first) sorting ties alphabetically.

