#### **10.12.2 Vital signs**

Vital signs (defined in section 8.11.4), including changes from baseline (defined in section 11.1.1), will be listed and summarized on the SAF for each parameter separately, using descriptive statistics

for continuous data. In the evaluation of the absolute changes from baseline, only subjects with both the baseline and specific time point assessment will be included.

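### The dosing footnote illustrates a 3-to-4-day interval with Monday and Wednesday (gaps of 2 and 5 days); with a Monday start, the SAP windows would drop 5 of 12 vital-sign records from the by-visit summary

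*Protocol*

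**What the plan says.** **Dosing schedule.** The footnote marked * under Protocol Table 3 (section 6.1) reads "Twice weekly dosing will occur every 3 to 4 days (e.g., every Monday and Wednesday", closes the bracket and adds a ±1 day window. The same footnote stands under SAP Table 1 (section 2.1.2). The other statements of the schedule are:

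- Protocol synopsis, Study Design: "twice a week on a 3/4-day schedule", with ±1 day attached. The placebo arm is described as "administered orally twice weekly (e.g., Tuesday/Friday) for 6 weeks".
- Protocol 5.5: "IMP will be administered twice a week, every 3 to 4 days".
- SAP 10.12.1.1 names the dosing days: "Week 1 D1 (Dose 1), Week 1 D5 (Dose 2), Week 2 D8 (Dose 3), Week 2 D12 (Dose 4"), and so on to D40 for dose 12.

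**Mapping of visits.** SAP Table 3 is headed "Scheduled Visit Window and Mapping of Assessments for Vital Sign, C-SSRS". In Weeks 2 to 6 the first weekly visit has a window from 1 day before to 2 days after its target (D8: 7 to 10; ...; D36: 35 to 38). The second has a window that opens 1 day before its target (D12: 11 to 13; ...; D40: 39 to EOT). EOT is the day of the last dose (SAP 11.1.1.3). SAP 2.1.3 states: "If a subject has two or more actual visits in the same visit window, the visit closest to the target day will be used". If two visits are equally far from the target, the later one counts. The same section keeps every assessment in the listings.

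**Use of the data.** Under SAP 10.12.2, vital signs "will be listed and summarized on the SAF for each parameter separately, using descriptive statistics". C-SSRS shares the Table 3 windows but is only listed (SAP 10.12.6).

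**The concern.** An example in a schedule footnote shows the intended calendar, and sites use that table to book visits. This one shows gaps that are not the stated interval. If ±1 day applies to the interval, 2 and 5 days are the outer limits (3 − 1 and 4 + 1), so the example turns both limits into the plan and leaves no slack. One further one-day shift could give a gap of 1 or 6 days.

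The example also interacts badly with the SAP. The Table 3 windows were built around a 4/3-day calendar. A second weekly visit only 2 days after Day 8, 15, 22, 29 or 36 still lies in the first visit's window, so the by-visit summary would omit a record from a visit that took place. The window for the second visit would stand empty.

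At stake are clarity about the calendar and the completeness of one descriptive safety summary.

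**Working it through.** **Step 1: gaps implied by each statement of the schedule**

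| Source | Dosing days | Gaps (days) |
|---|---|---|
| Footnote, stated interval | | 3 to 4 |
| Footnote, example | Monday, Wednesday | 2 and 5 |
| Synopsis, example | Tuesday, Friday | 3 and 4 |
| SAP 10.12.1.1 | D1, 5, 8, 12, ..., 36, 40 | 4 and 3 |

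The footnote's 3 to 4 days cannot be reproduced from its own example.

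**Step 2: mapping each calendar to SAP Table 3**

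Rules: assign each dosing day to its window; if two fall in one window, keep the one closest to target (the later if tied); EOT is the last dosing day.

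| Calendar | Days | Records dropped |
|---|---|---|
| Monday/Wednesday, Monday start | 1, 3, 8, 10, 15, 17, 22, 24, 29, 31, 36, 38 | 5 of 12 (Days 10, 17, 24, 31, 38) |
| Monday/Wednesday, Wednesday start | 1, 6, 8, 13, 15, 20, ..., 36, 41 | 0 |
| Tuesday/Friday, Tuesday start | 1, 4, 8, 11, 15, 18, ..., 36, 39 | 0 |
| Tuesday/Friday, Friday start (the SAP days) | 1, 5, 8, 12, 15, 19, ..., 36, 40 | 0 |

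In the first row, Week 2 runs as follows. Days 8 and 10 both lie in 7 to 10. The distances from target are |8 − 8| = 0 and |10 − 8| = 2, so Day 8 is kept and Day 10 is not used. The D12 window stays empty. Weeks 3 to 6 repeat this. Week 1 loses nothing, because Day 3 has the D5 window (2 to 6) to itself.

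**Step 3: when a record is lost in general**

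The condition is that both weekly visits fall in one first-visit window. For Week 2:

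| Visit days | Gap | Result |
|---|---|---|
| 8 and 10 | 2 | Day 10 dropped |
| 7 and 9 | 2 | tie at distance 1: Day 7 dropped |
| 7 and 10 | 3 | Day 10 dropped |
| 9 and 11 | 2 | none dropped |
| 8 and 11 | 3 | none dropped |

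A 2-day gap is therefore neither necessary nor sufficient. Tuesday/Friday with a Tuesday start loses nothing on its nominal days, but a second visit held one day early (Day 10 instead of 11) brings back the 8/10 case.

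**Step 4: the other reading of ±1 day**

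If ±1 day is counted from the SAP's nominal days, doses 2 to 12 can each move by −1, 0 or +1 day, which gives 3^11 = 177,147 combinations. None loses a record. On this reading Day 10 is 2 days before D12 and so out of window.

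**Step 5: efficacy ratings**

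AISRS and CGI-S follow SAP Table 2, with windows of Days 2 to 21 for Week 2 and Day 35 to EOT for Week 6. On the Monday-start calendar the ratings fall on Day 8 (third dosing visit) and Day 38 (before the final dose). Both are inside their windows.

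**The case against.** The case against giving this weight is fair in several respects.

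- The footnote allows ±1 day, and the synopsis attaches that tolerance to the 3/4-day schedule, so gaps of 2 and 5 days can be read as tolerated. This stands: a reader should not infer that Monday/Wednesday dosing breaches the protocol. The fault is in using the two limits as the illustration.
- The synopsis and Protocol 5.5 state the interval correctly, and the SAP visit labels run 4 and 3 days, so sites may never use the example. This also stands. The documents do not show how often it would be followed.
- The loss depends on the reading of ±1 day. The schedule's column headings attach the tolerance to visits, and against the SAP's nominal days no permitted visit is lost. The synopsis supports the interval reading. The documents do not settle which applies, so the loss has to be stated as conditional.
- A reader might infer that every 2-day gap costs a record. The windows do not support that: Days 9 and 11, or a Wednesday start, lose none.
- A reader might also infer lost efficacy data or a biased safety comparison. Nothing supports this. The AISRS windows are wide, the vital-sign summary is descriptive, Protocol 13.6.7 plans no safety inference, and the same windows apply to both arms.

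The contradiction within the footnote remains, and so does the mapping result for a Monday start.

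**Conclusion.** The footnote example is wrong as written in both documents. It contradicts its own sentence, the synopsis and the SAP dosing days, and this rests on calendar arithmetic alone.

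Its consequence is conditional. A site that took the example as its calendar with a Monday start would lose 5 of 12 vital-sign records per completing subject from the by-visit summary, one in each of Weeks 2 to 6. That figure assumes the first weekly dose on Days 1, 8, ..., 36, the Table 3 windows as printed, and no other shifts. More generally, a record is lost whenever both weekly visits fall in one first-visit window. If ±1 day is counted from the SAP days, that does not happen for any permitted visit.

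The frequency cannot be estimated from the documents. The printed row affected is not settled either, because Table 3 labels visits by day while Layout T22 presents vital signs by week. All records remain in the listings. The impact is minor.

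**What to change.** 1. In the footnotes to Protocol Table 3 and SAP Table 1, replace the example with Tuesday/Friday (as in the synopsis) or Monday/Thursday. Both give gaps of 3 and 4 days.
2. In SAP 2.1.3 and Table 3, assign vital signs taken at dosing visits by eCRF dosing visit (dose number), as SAP 10.12.1.1 does for adverse events. Each dosing visit then keeps its own row whatever the gap. The footnote correction alone would not ensure this, as the early Tuesday/Friday visit in Step 3 shows.

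Moving the window limits instead (for example D8 to 7–9 and D12 to 10–13, and likewise in later weeks) is not recommended. Days 7 and 9 would still share a window, and Days 10 and 13, which lose nothing now, would begin to lose one. Take every calendar with the first weekly dose within ±1 day of Days 8, 15, ..., 36 and all gaps of 2 to 5 days: 308,320 patterns. The current windows lose at least one record in 213,048 of them, and the shifted windows still do so in 88,941. These are counts of patterns, not probabilities.

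The cost is a few words in two footnotes and one mapping rule. No new data are needed.
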